Hypersensitivity reaction labs (tryptase, IgE, C5b-9, chemistry, hematology, and urinalysis)	Х					$\leftarrow X^i\!\!\rightarrow$					
Concomitant medications			←Monitor	continual	ly after ICF is	signed→					
Adverse events review/evaluation	$\leftarrow Monitor continually after ICF is signed \rightarrow$										

Note: When scheduled at the same timepoint, the triplicate ECG should be performed first, followed by vital signs assessments, and then PK/PD sampling.

^a All postdose timepoints are relative to the start of the IV infusion/time of the SC injection (ie, time 0 hr) except the ECG, PK/PD sample, and infusion site evaluation performed/collected at the EoI (see footnote d).

^b Only if the Investigator approves the day prior as an Outpatient Visit.

^c Each 12-lead ECG will be performed in triplicate (sequentially within a 15-minute period) and should not be assessed after any major meal (ie, major meals should be withheld until after ECG assessments). At least the last of the 3 predose triplicate 12-lead ECG will be performed within half an hour prior to dosing. The ECGs at 2, 6, and 12 hours postdose have a window of \pm 30 minutes.

^d ECG and PK/PD (in that order) performed/collected at EoI (t_{max}) each have a window of + 15 minutes.

Protocol Amendment 5 10 Mar 2022

ALXN1850-HPP-101

- ^e Vital signs will be measured every 15 minutes for the first hour after dosing, with a window of \pm 5 minutes. Other vital signs measurements have a window of \pm 15 minutes.
- ^f A window of ± 30 minutes from each postdose time point is permitted for all PK/PD timepoints except EoI. Predose PK/PD windows are -1 hour (SC doses) and -3 hours (IV dose).
- ^g Injection/infusion site evaluations will be performed during the infusion, after I/EoI, and then within 15 minutes (+ 5 minutes) after I/EoI. The rest of the timepoints have a window of \pm 15 minutes.
- ^h Predose and postdose abbreviated PEs are allowed at the predose or dosing day, and on the day after dosing or 2 days after dosing, depending on when the participant is admitted and discharged.
- ⁱ If a hypersensitivity reaction is suspected, samples should be collected as soon as possible (within 1 hour of the reaction) and again at 2 and 8 hours (+ 1 hour window each) after the 1st sample. The Day 1 predose sample will only be analyzed for participants with a reported suspected hypersensitivity reaction at any time following the first dose.

Abbreviations: ADA = antidrug antibody; C5b-9 = terminal complement complex C5b-9; CRIM = cross-reactive immunological material; ECG = electrocardiogram; EoI = end of infusion; hr = hour; ICF = informed consent form; IgE = immunoglobulin E; IV = intravenous; min = minutes; NAb = neutralizing antibody; PA = pyridoxic acid; P1NP = N-terminal propertide of type I procollagen; PD = pharmacodynamics; PE = physical examination; PK = pharmacokinetics; PL = pyridoxal; PLP = pyridoxal 5'-phosphate; PPi = inorganic pyrophosphate; CTX-1 (sCTX) = serum Ctelopeptide cross-link of type 1 collagen; SC = subcutaneous; t_{max} = time to maximum observed plasma concentration

Page 28 of 97	
Alexion Confidential	

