Note: Participants who complete the EoT assessments but withdraw/are withdrawn prior to completion of the end-of-study assessments will be considered "completed" and do not require replacement if they completed all prior PK/PD sampling within window and received all doses per the SoA. Participants who withdraw/are withdrawn prior to the end-of-treatment visit should have the end-of-treatment assessments performed, if possible, and will be replaced unless

3 participants in their cohort have already "completed" or are on track to "complete".

^a Visits designated "I/O" may be performed Inpatient or Outpatient at the Investigator's discretion.

^b All postdose timepoints are relative to the start of the IV infusion/time of the SC injection (ie, Time 0) except the vital signs measurements, PK and PD sample, and infusion site evaluation performed/collected at the EoI (see Table 3).

° Signed and dated IEC-approved ICF must be obtained before any study-specific screening procedures are performed.

^d If available, historical results are acceptable, and a confirmatory test is not required.

^e Female participants who claim postmenopausal status will have an FSH test to confirm status.

^f A negative drug screen is required for participant enrollment. Results from drug screens collected at timepoints prior to dosing (Days -1, 14, 21, 28) are not required to confirm a negative result prior to dosing. The drug screen results received after sampling will be noted, and if positive, the participant will be

ALXN1850-HPP-101

Protocol Amendment 5 10 Mar 2022

discontinued from the study. If negative, the results will serve as clearance to proceed with dosing for future pre-dosing days. A positive drug test result for a non-prescribed substance received at any visit will lead to discontinuation

- ^g Pregnancy test must be performed on all participants of child-bearing potential at the specified time points. Additional pregnancy tests may also be performed at any time at the Investigator's discretion.
- ^h Predose and postdose abbreviated PEs are allowed at the predose or dosing day, and on the day after dosing or 2 days after dosing, depending on when the participant is admitted and discharged.
- ⁱ If a potential participant is rescreened, these assessments do not need to be performed again unless more than 12 months will have elapsed between each test and enrollment.

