- ^j A window of ± 30 minutes from each time point is permitted for PK/PD timepoints except the PK sample collected at end of infusion (+ 15 minutes). Predose PK/PD windows are -1 hour (SC doses) and 3 hours (IV dose). For all assessments, their window and the visit window should not be calculated together to determine the permitted assessment time.
- ^k Asfotase alfa ADA and NAb will only be tested in participants who have previously received asfotase alfa. Participants do not need to be retested for ADAs and NAbs if they are re-screened.
- ¹ Each 12-lead ECG will be performed in triplicate (sequentially within a 15-minute period) and should not be assessed after any major meal (ie, major meals should be withheld until after ECG assessments). All ECGs should be performed before the vital signs assessment and PK/PD sampling (in that order if 1 or both of the latter are also scheduled during an ECG timepoint). Each ECG shown in this table has a window of \pm 30 minutes.
- ^m Injection/infusion site evaluations will be performed within 15 minutes (\pm 5 minutes) after injection/EoI and \pm 15 minutes of the rest of the timepoints.

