5.2. Exclusion Criteria

Medical Conditions

- 1. Primary or secondary hyperparathyroidism or hypoparathyroidism.
- 2. Current or recurrent concomitant disease that could affect clinical assessments or clinical laboratory evaluations.
- 3. Current or relevant history of physical or psychiatric illness that is not stable or may require a change in treatment, use of prohibited therapies during the study, or make the participant unlikely to fully comply with the requirements of the study or complete the study, or any condition that presents undue risk from the study drug or study procedures.

- 4. Any other significant disease or disorder which, in the opinion of the Investigator, may put the participant at risk.
- 5. ECGs showing a PR value of less than 120 ms or greater than 240 ms, QRS > 110 ms, and QT interval corrected using Fridericia's formula (QTcF) > 450 ms for men and QTcF > 470 ms for women at Screening. If the results of the first triplicate ECG are abnormal, 2 additional triplicate ECGs will be performed. Both of the subsequent triplicate ECGs must be within normal ranges or the participant is not eligible for the study.
- 6. Heart rate > 120 beats per minute (bpm) at Screening.
- Human immunodeficiency virus (HIV) infection (evidenced by HIV type 1 or type 2 antibody titer), acute or chronic hepatitis B virus (HBV) infection (evidenced by hepatitis B surface antigen), or acute or chronic hepatitis C virus (HCV) infection (evidenced by antibody titer)
- 8. Fracture within 12 weeks of screening.
- 9. History of significant allergic reaction (eg, anaphylaxis or angioedema) to any product (eg, food, pharmaceutical).

Prior/Concomitant Therapy

- 10. Use of nonprescription/ over-the-counter medications, including herbal remedies and supplements, within 7 days before dosing Day 1, except with prior approval of Alexion.
- 11. Use of vitamin B6 (including vitamin supplements that contain vitamin B6) within 2 weeks prior to screening.
- 12. Oral bisphosphonate use within 6 months (depending on the half-life of the drug as assessed by the Investigator) and IV bisphosphonate use within 12 months prior to screening.
- 13. Asfotase alfa use within 6 months or positive for asfotase alfa antidrug antibody (ADA)/neutralizing antibodies (NAbs) [only required for patients with a history of asfotase alfa use].
- 14. Teriparatide/parathyroid hormone (PTH) analog use within 2 months prior to screening.

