5.4. Screen Failures

Screen failures are defined as participants who consent to participate in the clinical study but are not subsequently entered into the study. A minimal set of screen failure information is required to ensure transparent reporting of screen failure participants to meet the Consolidated Standards of Reporting Trials publishing requirements and to respond to queries from regulatory authorities. Minimal information includes demography, screen failure details (eg, failed eligibility criteria), and any AEs, including any serious adverse events (SAEs) and any related concomitant medication, occurring during the Screening Period.

Individuals who do not meet the criteria for participation in this study (screen failure) due to a reason that is expected to resolve or has resolved, may be rescreened based on discussion and agreement between the Investigator and the Medical Monitor. Investigational sites are permitted to rescreen participants who do not meet inclusion/exclusion criteria.

Page 42 of 97	
Alexion Confidential	

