6.5.2. Disallowed Medicine and Therapy

Use of vitamin B6 (including vitamin supplements that contain vitamin B6) must be discontinued at least 2 weeks before Screening.

Use of oral bisphosphonate and IV bisphosphonate must be discontinued 6 months and 12 months, respectively, before Screening. Treatment with strontium or sclerostin inhibitors must be discontinued at least 6 months before the first dose of study drug. Use of teriparatide/ PTH analog must be discontinued at least 2 months before Screening.

Use of asfotase alfa within 6 months of Screening and throughout the study is prohibited.

A concomitant procedure is any therapeutic intervention (eg, surgery/biopsy, physical therapy) or non-study diagnostic assessment (eg, blood gas measurement, bacterial cultures) performed from the time the participant is screened for the study until the last study visit. Concomitant procedures are not allowed unless medically indicated.

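### The re-screening waiver in footnote k lets exclusion 13 be met on an asfotase alfa antibody result that predates the participant's last asfotase alfa exposure

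*Protocol*

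**What the plan says.** Four parts of the protocol bear on this point.

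- **Eligibility.** Exclusion 13 in section 5.2 has two limbs, recent use and antibody status: "Asfotase alfa use within 6 months or positive for asfotase alfa antidrug antibody", extended to neutralizing antibodies. Section 6.5.2 sets the reference date for the first limb: "Use of asfotase alfa within 6 months of Screening and throughout the study is prohibited".
- **Testing.** Footnote k to Tables 1 and 2 opens: "Asfotase alfa ADA and NAb will only be tested in participants who have previously received asfotase alfa". The tables schedule this test in the Screening column only. Protocol section 8.9 and SAP section 11 also place it at Screening. Neither gives a period for which a result stays valid.
- **Waiver.** The same footnote continues: "Participants do not need to be retested for ADAs and NAbs if they are re-screened". The wording is identical in both tables and carries no qualifier.
- **Re-screening.** Section 5.4 allows it for people who failed "due to a reason that is expected to resolve or has resolved, may be rescreened", with the agreement of the Investigator and the Medical Monitor. It adds: "Investigational sites are permitted to rescreen participants who do not meet inclusion/exclusion criteria". It states no maximum number and no maximum interval.

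For comparison, footnote i on the ophthalmological and renal assessments does limit reuse at re-screening: "these assessments do not need to be performed again unless more than 12 months will have elapsed between each test and enrollment".

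**The concern.** The antibody limb of exclusion 13 is informative only if the sample reflects all the asfotase alfa a person has received. Footnote k breaks that link at re-screening. It looks only at whether a test was done before, not at whether the person has been exposed since.

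Antibody status can change with further exposure, which is why the protocol tests people with past use at all. A negative result from before a further course of treatment does not describe the person who is about to be enrolled. A site could follow every instruction as written and still enrol someone whose current asfotase alfa antibody status is unknown.

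This is a first-in-human study. It cites immunogenicity as a reason for its choice of population, and section 2.3.1 lists antibody formation and hypersensitivity among the potential risks. Its cohorts are very small, so an eligibility rule that can give the wrong answer deserves correction even if it is seldom used.

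**Working it through.** No sample size, power or error rate is involved and the plan states no figure to reproduce. The check is a reading of the passages together, plus timeline arithmetic.

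**Which test does the waiver cover?** The footnote says ADAs and NAbs without naming the drug. In the Screening column of Tables 1 and 2 the only such test is the one for asfotase alfa. ALXN1850 antibodies are first sampled predose on Day 1 (Table 3). The waiver therefore falls on the test that feeds exclusion 13.

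**Does anything else force a new sample?** Sections 5.2, 5.4, 6.5.2 and 8.9 and SAP section 11 were compared. The 6-month limb controls how recent the last dose may be. No section ties the antibody sample to that dose.

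**Timeline.** Let the negative sample be taken at time T0, in months. Assume that at re-screening the 6-month limb is counted back from the re-screening date.

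1. *Asfotase alfa continued or resumed after the sample.* The last dose is at T0 + x, with x > 0. The use limb is met from T0 + x + 6 onward. Footnote k lets the T0 result stand, so the result is older than the last dose by x. As an illustration, x = 2 gives re-screening from T0 + 8 on a result that predates the last dose by 2 months.
2. *No further dosing.* The last dose was y months before the sample, with 0 < y < 6. The person fails the use limb, waits, and is re-screened from T0 + (6 − y). With y = 5 that is T0 + 1. The sample was taken after the last dose and does not predate it.
3. *No earlier sample.* Someone who failed before being sampled, or who first received asfotase alfa after the initial screening, has nothing to be retested, so the test is still due.

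Only the first case produces the problem.

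**Would an age limit alone close it?** Suppose the 12 months of footnote i also applied to the antibody result, with re-screening and enrolment treated as the same date. Case 1 then requires x + 6 ≤ 12, so x ≤ 6. Dosing for up to about 6 months after the sample would still pass. An age limit narrows the gap. A condition on exposure closes it.

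**Weight of one participant.** With about 5 per cohort, 1/5 = 20%. At the minimum of 3 completers, 1/3 = 33%.

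**The case against.** The strongest reply is that the case is rare and that other safeguards surround it. The footnote permits a site not to retest; it does not forbid retesting. Re-screening needs agreement from the Investigator and the Medical Monitor. Section 5 and inclusion 3 select people who do not currently need asfotase alfa and are not expected to need enzyme replacement afterwards, so returning to it between screenings would be unusual. Eligibility waivers are not allowed, and section 10.2 lets the Investigator add tests. All of this stands and makes the case less frequent. None of it requires a new sample after new exposure.

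A reader might infer more than the documents support:

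- *That the study results would be contaminated, or a hypersensitivity reaction made likely.* The documents say the two drugs share a mechanism of action. They do not say that antibodies to one react with the other. ALXN1850 antibodies are sampled before the first dose, SAP section 11 separates pre-existing from treatment-emergent and treatment-boosted responses, and the SAP repeats its main PK, PD and adverse event summaries by ADA status. Exclusion 9 and the frequent vital signs after dosing address allergic risk separately. The Day 1 sample aids interpretation but is not an eligibility test.
- *That anyone first failed for recent use carries a result at least 6 months old.* Case 2 above shows that it can be about 1 month old.
- *That section 8.9 concedes the asfotase alfa result is unreliable with drug in circulation.* That passage concerns ALXN1850 concentration and ALXN1850 antibodies.
- *That the 12-month limit for imaging should be carried over.* It answers a different question and would not close the gap by itself.

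**Conclusion.** The point holds in a limited form. As written, footnote k can let a previously treated person meet the antibody limb of exclusion 13 on a result that predates their last asfotase alfa exposure. This is a stated rule that can give the wrong eligibility answer, not an omitted detail.

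It requires one sequence: past use, a negative sample, screen failure, asfotase alfa continued or resumed after that sample, at least 6 months off drug, and re-screening without a voluntary retest. The documents do not say how many people might follow it; the range runs from none to a few. Someone admitted this way would not necessarily be antibody positive; their status would simply be unknown. The conclusion assumes that a sample was taken at the failed screening and that the 6 months are counted back from the re-screening date. It does not rest on cross-reactivity. The correction is worth making because it costs little and the cohorts are small.

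**What to change.** Reconcile footnote k in Tables 1 and 2 with exclusion 13. State that the re-screening waiver applies only if no asfotase alfa has been taken since the previous asfotase alfa antibody sample, and that otherwise the ADA and NAb tests are repeated at re-screening. Whether also to set a maximum age for the earlier result is for the sponsor to decide; the documents do not point to a particular value.

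The cost is one conditional clause in two footnotes, made in an amendment, and one extra serum assay for each re-screened participant who has taken asfotase alfa since the last sample. Re-screening already involves blood tests, so the sample can be drawn at the same visit. Re-screened participants with no such exposure are unaffected.

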2. INTRODUCTION

2.1. Study Rationale

ALXN1850 is a human recombinant TNSALP-Fc-deca-aspartate fusion protein being developed as an investigational ERT to address the underlying cause of HPP by replacing the defective TNSALP enzyme. It is a soluble glycoprotein comprised of 2 polypeptide chains of 724 amino acids made from the catalytic domain of human TNSALP (SwissProt, P05186), the human Ig G2/4 Fc domain (SwissProt P01859 and Genebank K01316; to facilitate purification and extend half-life), and a deca-aspartate peptide (to target the bone). ALXN1850 is designed for SC administration. Nonclinical pharmacology, PK, and toxicology studies of ALXN1850 have been conducted to support the clinical testing of ALXN1850 in humans. The Phase 1 FIH study is designed to evaluate the safety, tolerability, PK, and PD of ALXN1850 when given IV and SC to adults with HPP.

This FIH study will enroll adult participants with HPP who have a confirmed mutation for the gene (*ALPL*) that encodes the enzyme TNSALP, resulting in the presence of decreased serum alkaline phosphatase (ALP) activity and elevated serum pyridoxine and inorganic pyrophosphate, which are the genetic and biochemical hallmarks of the disease. The characteristics of this population represent patients with HPP who currently do not require ERT but could qualify for future Phase 2 and Phase 3 studies, depending on the disease burden. This study has been designed to minimize risk to participants; it is a study with strict inclusion/exclusion criteria and there is a robust safety monitoring and risk mitigation plan in place to address potential safety and tolerability findings. Because of the potential for immunogenicity, this study will enroll participants with HPP who are not anticipated to require continued treatment with ERT, based on their signs and symptoms, and the Investigator's clinical assessment of their current condition.

ALXN1850 and asfotase alfa, the only approved treatment for HPP, have the same mechanism of action and address the underlying cause of HPP by replacing the defective enzyme, thus reversing the mineralization defects of the skeleton and improving systemic manifestations of HPP. ALXN1850 differs from asfotase alfa in the following ways: it is altered by an amino acid change to enhance substrate hydrolysis by its active site; its Fc domain is an IgG2/4, to improve half-life and bioavailability; 2 N-linked glycans have been removed from each TNSALP polypeptide chain via asparagine to glutamine mutations, and other enhancements to its glycan profile which should alter the PK of the active moiety and increase its exposure and half-life.

Currently, the recommended dosage regimen of asfotase alfa for the treatment of pediatric-onset HPP is 6 mg/kg per week administered SC as either 2 mg/kg 3 times per week, or 1 mg/kg 6 times per week. However, patients using asfotase alfa are burdened with a high rate of injection site reactions and an inconvenient administration frequency (3 to 6 times per week). ALXN1850 is a next-generation HPP therapy developed with the intent to deliver a molecule with equivalent potency and improved activity compared to asfotase alfa, providing higher exposure, longer half-life, and better bioavailability. These improvements may address current asfotase alfa limitations and support lower doses and longer dosing intervals. Patient experience is expected to improve by reducing injection volumes and dosing frequency, which may also translate to fewer injection site reactions and higher patient compliance.

2.2. Background

A detailed description of the chemistry, pharmacology, and toxicology data available for ALXN1850 is provided in the Investigator's Brochure (IB).

2.2.1. Hypophosphatasia

Hypophosphatasia is a rare, inherited, metabolic disease caused by deficient activity of the TNSALP, typically due to loss-of-function mutation(s) in the *ALPL* gene. TNSALP is a glycosylphosphatidylinositol anchored ectoenzyme, which although widely expressed, is expressed at particularly high concentrations on the surface of osteoblasts. During normal bone mineralization, TNSALP dephosphorylates inorganic pyrophosphate (PPi), producing inorganic phosphate (Pi). Inorganic phosphate then precipitates calcium (Ca²⁺) in the extracellular matrix to form calcium phosphate that is then transformed into hydroxyapatite crystals, which give bones their strength and rigidity. Other known endogenous substrates for ALP include pyridoxal-5'-phosphate (PLP) and phosphoethanolamine (PEA) (Whyte, 2012; Whyte, 1994).

In HPP, low TNSALP activity leads to extracellular accumulation of PPi, which inhibits bone mineralization by blocking hydroxyapatite crystal formation (Russell, 1965; Fleisch, 1966; Rockman-Greenberg, 2013). Consequently, Ca²⁺ and PPi accumulate in the bloodstream, causing disturbances in calcium/phosphate homeostasis (Linglart, 2016). In addition, TNSALP dephosphorylates PLP, the circulating form of vitamin B₆, producing pyridoxal (PL), which crosses the blood-brain barrier and is rephosphorylated into PLP, where it plays an important role in the synthesis of multiple neurotransmitters (Whyte, 1994; Whyte, 2012). The role of PEA is not completely understood but may be a component of the phosphatidylinositol-glycan linkage apparatus that couples TNSALP and many other proteins to cell surfaces.

As a direct result of deficient TNSALP, progressive damage to vital organs along with other clinical sequelae may occur; including deformity and softness of bones (rickets-like bone deformities and osteomalacia), fractures and pseudofractures, pain, profound muscle weakness, respiratory failure (primarily in infants), seizures (mainly in infants), impaired renal function, impaired mobility, and dental abnormalities. Hypophosphatasia is associated with a high-fracture and orthopedic/dental surgical burden, pain, need for assistive walking devices (due to impaired mobility), and impairments in activities of daily living in children and adults. Severe disease associated with rachitic changes in the chest often lead to diminished respiratory function (due to lack of rib cage support) and risk of ventilator dependence and premature death (mainly in infants). The deficiency of PLP in the central nervous system in patients with HPP can result in infantile seizures which are responsive to pyridoxine (Baumgartner-Sigl, 2007; Whyte, 1985).

